2.4.3 Primary efficacy analysis

[figure not shown]
The primary efficacy analysis is test of non-inferiority of *Restylane® Kysse* to control treatment in the ITT and PP analysis sets, using the confidence interval approach and a non-inferiority margin of 0.5 units. [REDACTED]

Difference between treatments means (control – *Restylane® Kysse*), and the corresponding 2-sided 95% CI, will be calculated and presented for each of the 2 co-primary endpoints using the Student's t-statistic.

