1.1 Background

1.1.1 Study design

This is a randomized, controlled, evaluator-blinded, multi-center study to evaluate the effectiveness and safety of *Restylane® Kysse* for lip augmentation and correction of perioral rhytids.

Approximately 280 subjects will be randomized in a 2:1 ratio of treatment to control and treated. Approximately 187 subjects will be treated with *Restylane® Kysse* and 93 subjects will receive the control in the lips and perioral rhytids and will be followed for 48-weeks.

Investigator blinding will be accomplished by using a Treating Investigator to administer the treatments and a Blinded Evaluator, to whom randomization and treatment are concealed, to conduct the blinded assessments.

Safety assessments will be performed by non-blinded personnel. Eligible subjects randomized to receive treatment will be injected by the Treating Investigator at Day 1.

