1.1.2 Number of subjects and randomization

Approximately 280 subjects will be randomized to treatment or to control in a 2:1 ratio (treatment: control) stratified by FST (I-III, IV or V-VI) to achieve a total sample size of 234 evaluable subjects (156 randomized to *Restylane® Kysse*, and 78 to *Juvéderm Volbella® XC*). Subjects in the FST=I-III stratum will be further stratified by study centers; subjects in the FST=IV, or FST=V-VI strata will not be further stratified by study centers due to the small sample size.

Before starting the study, a randomization list will be prepared under the supervision of a designated statistician. Randomization will be performed using an Interactive Response System by assigning each subject to *Restylane® Kysse* or the control according to the randomization list.

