2.1 General methods

All statistical analyses, including summary tables and data listings, will be performed using the SAS® system (Version 9.3 or higher). Confidence intervals (CIs) will be two-tailed and constructed at a confidence level of 95%. P values will be two-sided and performed at a significance level of 5%.

All study data including observed and derived variables (e.g., change from baseline, response status) used in the summaries of analyses will be presented in by-subject listings. In general, efficacy, safety, demography, subject characteristics, and treatment related variables will be presented using descriptive statistics. For categorical parameters, the number and percentage of subjects in each category will be presented. The denominator for percentage will be based on the number of observations at that time point (i.e. observed cases). For continuous parameters, descriptive statistics will include number of observations, mean, standard deviation (SD), median, and range. Graphs will be used as appropriate.

Any change made to the finalized statistical analysis plan (SAP) after database lock will be documented in the Clinical Study Report (CSR).

For the primary analysis, non-inferiority will only be demonstrated if the CI is entirely below 0.5 for both co-primary endpoints in both the ITT and PP populations. Similarly, superiority will only be demonstrated if the lower confidence limit is entirely below 0 for both co-primary endpoints in both the ITT and PP populations. Therefore no multiplicity adjustment for Type I error is required.

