2.7 Determination of Sample Size

Accounting for approximately 15% drop-outs and non-evaluable subjects due to protocol deviations at week 8, a total of approximately 280 subjects will be randomized in the study. It is expected that the number of randomized subjects will be similar across the study sites.

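### With 2:1 allocation, SAP 2.4.3 should name the unequal-variance t interval for the co-primary comparisons, because Student's t normally pools the variances

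*SAP*

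**What the plan says.** SAP 2.4.3 tests non-inferiority by confidence interval with "a non-inferiority margin of 0.5 units". The interval for control minus Kysse is calculated "for each of the 2 co-primary endpoints using the Student's t-statistic". The visible text does not say whether the variance is pooled. A redacted stretch follows the sentence that states the margin.

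SAP 2.1 makes this interval the whole decision: "non-inferiority will only be demonstrated if the CI is entirely below 0.5 for both co-primary endpoints in both the ITT and PP populations". The superiority rule in the same section uses the same interval, and SAP 2.4.5 carries the method into the subgroup analyses.

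On allocation, SAP 1.1.2 specifies "a 2:1 ratio (treatment: control) stratified by FST (I-III, IV or V-VI) to achieve a total sample size of 234 evaluable subjects", split as 156 Kysse and 78 control. SAP 1.1.1 gives about 187 and 93 randomized.

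The visible text has no SD for either arm, no variance check and no unequal-variance alternative. The only visible sensitivity analysis of the primary endpoint concerns missing data (SAP 2.4.2). The protocol supplied with this SAP describes an open-label study of 50 to 60 subjects without a reference product, so it neither supports nor contradicts the point.

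**The concern.** The pooled variance weights each arm by its degrees of freedom, so the larger Kysse arm dominates it. The true standard error of the difference depends more on the smaller control arm. When the two SDs differ, the pooled standard error is therefore wrong, and the direction depends on which arm is more variable. If control is more variable, the interval is too narrow and a product exactly at the margin passes more often than 2.5% of the time. If control is less variable, the interval is needlessly wide and power is lost. Equal allocation would largely remove the problem; 2:1 allocation does not. Because the claim turns on whether this interval lies below 0.5, its width bears on the error rate of each component test.

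**Working it through.** **Inputs from the SAP.** Margin 0.5; two-sided 95% CI, so one-sided 2.5% for non-inferiority; 2:1 allocation; 156 and 78 evaluable; about 15% loss (SAP 2.7).

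**Input that is assumed.** r, the control SD divided by the Kysse SD, with the Kysse SD set to 1.

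**The plan's own figures.** 234/0.85 = 275.3, so 276, against about 280 stated (a gap of 1.4%). 234 × 2/3 = 156 and 234/3 = 78. 280 × 2/3 = 186.7 and 280/3 = 93.3. The stated numbers hang together. The 234 itself cannot be rebuilt, since no SD or power is visible.

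**Formulas.**
- Pooled variance: s_p² = (155 + 77r²)/232
- Variance that the pooled interval uses: V_pooled = s_p² × (1/156 + 1/78) = s_p² × 0.01923
- Actual variance: V_true = 1/156 + r²/78
- False non-inferiority rate per endpoint, true difference at the margin: 1 − Φ(1.96 × √(V_pooled/V_true))

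| r | s_p² | V_pooled | V_true | √ratio | Rate (formula) | Rate (simulated, pooled) |
|---|---|---|---|---|---|---|
| 0.8 | 0.8805 | 0.01693 | 0.01462 | 1.076 | 1.7% | 1.7% |
| 1.0 | 1.0000 | 0.01923 | 0.01923 | 1.000 | 2.5% | 2.5% |
| 1.2 | 1.1460 | 0.02204 | 0.02487 | 0.941 | 3.25% | 3.2% |
| 1.5 | 1.4149 | 0.02721 | 0.03526 | 0.878 | 4.3% | 4.2 to 4.3% |

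For r = 1.5: 1.96 × 0.878 = 1.72, and 1 − Φ(1.72) = 4.3%. Two-sided coverage is about one minus twice the rate: roughly 96.5%, 95.0%, 93.5% and 91.5% down the table. The simulations used normal data.

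**Checks.**
- At 187/93 the results barely change (4.2% at r = 1.5).
- At 117/117, V_pooled = ((1 + r²)/2) × (2/117) = (1 + r²)/117 = V_true, and the simulated rate stays at about 2.5% at every ratio. The 2:1 allocation is what creates the exposure.
- The Welch-Satterthwaite interval at 156/78 gave 2.47% to 2.51% for every ratio from 0.5 to 2.

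**From one endpoint to the trial.** Both endpoints must pass, so the trial-level rate cannot exceed the rate of an endpoint that sits at the margin. It approaches that rate when the other endpoint is well inside. With both at the margin and r = 1.5, an approximate joint simulation of the pooled test gave about 1.0% at an assumed correlation of 0.5 and 2.0% at 0.8. Requiring PP as well can only lower these.

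**Power** (true difference 0, Kysse SD assumed 1.0, per endpoint). With equal SDs the pooled and Welch intervals differ by under about 0.1 point, both near 94.8%. At r = 0.8 Welch is ahead, 98.5% against 97.8%.

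**The case against.** A reader might infer that the trial's type I error is inflated. The documents do not support that, for four reasons.

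- **The form is not settled.** The SAP names Student's t without saying pooled, and redacted text in the same section could specify it. This stands; the pooled reading is the ordinary one, not a certain one.
- **Nothing shows unequal SDs, still less a more variable control arm.** The comparator is a named product injected in the same areas, subjects are randomized, and the evaluator is blinded. A ratio of 1.5 means a control variance 2.25 times that of Kysse. If control is less variable, the pooled interval is conservative. The absence of SDs cannot be held against the plan either, because the sample-size and endpoint sections are largely blacked out. All of this stands.
- **The rates are per endpoint.** The rule of two endpoints in two populations can bring the trial-level rate below 2.5% even at r = 1.5. This stands when both endpoints are at the margin. It gives little protection when only one is, and PP overlaps ITT too heavily to be counted on to restore the level.
- **The pooled t is a standard method, so this is preference.** This stands in part: using it is not a defect in itself. But variance equality cannot be known when the SAP is fixed, SAP 2.1 relies on the joint rule to do without multiplicity adjustment, which presumes that each component test holds its level, and the more robust interval costs almost nothing.

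**Conclusion.** The point holds as a low-cost improvement, not as a proven error. On the ordinary reading of Student's t, the co-primary intervals depend on an equal-variance assumption that 2:1 allocation does not protect. The consequence is conditional: about 1.7% to 4.3% per endpoint in place of 2.5%, for assumed SD ratios of 0.8 to 1.5, with the true difference at the margin. For the trial-level claim these are upper bounds. The figures say nothing about which ratio will occur, and they fall away if the redacted part of 2.4.3 already specifies an unequal-variance interval.

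**What to change.** In SAP 2.4.3, state that the two-sided 95% CI for control minus Kysse uses the unequal-variance (Welch-Satterthwaite) t interval for both co-primary endpoints, in ITT and in PP, unless the redacted text already says so. The subgroup analyses in 2.4.5 then follow automatically.

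The cost is one phrase; standard SAS t-test output already prints this interval. If the SDs are equal, the loss is under about 0.1 point of power per endpoint. If control is more variable, power is lower than with the pooled test, because the pooled test is then exceeding its nominal level. If control is less variable, power rises.

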2.4.4 Secondary analysis

CIs for responders mentioned below will be calculated using normal approximation.

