4.1 General outline

This is an open-label, phase IV, post-marketing study to evaluate aesthetic improvement and partner/subject satisfaction after treatment with Restylane Kysse, alone and in combination with Restylane Defyne and Restylane Refyne.

Approximately 50 to 60 subjects at 4 sites in Canada will be treated. Twenty subjects will be treated with Restylane Kysse in the lips only (Group A) and 30 to 40 subjects will be treated with Restylane Kysse in the lips and Restylane Defyne and/or Restylane Refyne in the facial wrinkles and folds (Group B). All injections will be per the IFUs. Optional touch-up treatment at Week 4 is allowed for all products injected at initial treatment.

The treating investigator will determine if a subject is placed in Group A or B based on the optimal outcome for the subject.

[figure not shown]
Adult women and men who have a steady relationship with a partner for 6 months and intend to undergo lip augmentation will be asked to participate in the study. Eligible subjects will be injected by the Treating Investigator at Day 1. If optimal correction of the lips or surrounding facial wrinkles and folds (if treated) is not achieved at the first treatment or if the aesthetic appearance could be further improved, a touch-up will be offered after 4 weeks; this decision should be agreed upon by the Treating Investigator and the subject. Touch-up treatment will not be performed if the subject has a disease or condition described in the exclusion criteria, or an ongoing treatment-related AE that in the opinion of the Treating Investigator would be worsened by a touch-up treatment.

The subjects will be treated to achieve optimal correction. Optimal correction is defined as the best possible aesthetic outcome as agreed to by the Treating Investigator and the subject.

The maximum volume recommended for both initial and touch-up treatments combined is 2.5 mL for Restylane Kysse, 6.0 mL for Restylane Defyne and 4.0 mL for Restylane Refyne.

Subjects will be contacted by telephone 72 hours after initial treatment and optional touch-up treatment (as applicable) and will have in-clinic follow up visits at 4 weeks and 8 weeks after the last treatment.

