2.4.2 Handling of missing data

Number of missing values will be summarized and reported as appropriate.

Missing data for the primary analysis [REDACTED] will be handled using the hot deck imputation method. Specifically, each missing value [REDACTED] at Week 8 (recipient) will be imputed with a non-missing (observed) value from a subject randomly selected from the same imputation class (donor). Imputation classes will be defined based on treatment group, FST (I-III, or IV-VI) and whether or not the subject met [REDACTED] criterion (Yes, No), [REDACTED]

[REDACTED] missing values will be imputed in a similar manner. Alternative imputation classes may be used if deemed necessary.

Impact of missing data on the primary analysis for Week 8 endpoint will be evaluated by performing sensitivity analysis based on the observed cases in the ITT population.

All other endpoints will be evaluated based on the observed cases in ITT, i.e. no imputations will be done.

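### SAP 2.4.4 sets responder confidence intervals by normal approximation; read as plain Wald intervals for single-arm rates, they fall short of 95% coverage at high rates, so Wilson (and Newcombe for differences) should be named

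*SAP*

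**What the plan says.** SAP 2.4.4 gives one readable sentence on interval estimation for responder endpoints: "CIs for responders mentioned below will be calculated using normal approximation". It does not say which form of normal approximation is meant. The endpoints it points to are not readable, so we cannot see whether the intervals are for each arm's rate, for a between-arm difference, or for both.

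SAP 2.1 fixes the level: "Confidence intervals (CIs) will be two-tailed and constructed at a confidence level of 95" per cent.

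The arm sizes come from two places. SAP 1.1.2 sets the randomised number "to achieve a total sample size of 234 evaluable subjects", split 156 Kysse and 78 control. SAP 1.1.1 states "Approximately 280 subjects will be randomized in a 2:1 ratio of treatment to control and treated", which it splits as about 187 and 93. Both sets matter, because SAP 2.4.2 says of endpoints other than the primary: "All other endpoints will be evaluated based on the observed cases in ITT, i.e. no imputations will be done". The denominators for responder rates may therefore lie anywhere between the evaluable and the treated numbers.

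The primary analysis is separate. In SAP 2.4.3, Student's t intervals for differences in means "will be calculated and presented for each of the 2 co-primary endpoints".

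**The concern.** In ordinary usage, a normal-approximation interval for a proportion is the Wald interval: the estimate plus or minus 1.96 estimated standard errors. Its standard error is computed from the observed proportion, so it shrinks towards zero as that proportion approaches 100%. In an arm of this size, the interval then becomes too narrow exactly where a successful aesthetic product might be expected to land. With no non-responders its width is zero. With one to three non-responders its upper limit exceeds 100% unless it is capped.

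At stake is the honesty of the error bars on secondary responder rates: a reported 95% interval that covers appreciably less often, or one that shows no uncertainty at all. No readable decision rule uses these intervals.

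**Working it through.** **Inputs.** Level 95%, z = 1.96 (SAP 2.1). n = 78 and 156 evaluable (SAP 1.1.2); n = 93 and 187 treated (SAP 1.1.1). True responder rates: none is documented, so a range of 50% to 99% is assumed.

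**The plan's own figure.** 234 evaluable with about 15% loss (SAP 2.7) gives 234 / 0.85 = 275.3, so 276, close to the stated 280. A 2:1 split of 280 gives 187 and 93. The arm sizes are internally consistent.

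**Formulas.** With p the observed proportion:

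- Wald: p ± z·√(p(1−p)/n)
- Wilson: [p + z²/(2n) ± z·√(p(1−p)/n + z²/(4n²))] / (1 + z²/n)

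Coverage at a true rate is the sum of the binomial probabilities of all counts whose interval contains that rate. It was enumerated exactly and averaged over 401 equally spaced rates per range.

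**Mean coverage of the nominal 95% Wald interval**

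| True rate | n=78 | n=93 | n=156 | n=187 |
|---|---|---|---|---|
| 50-80% | 94.3% | 94.4% | 94.6% | 94.7% |
| 80-90% | 93.2% | 93.5% | 94.1% | 94.3% |
| 90-95% | 91.7% | 91.8% | 93.1% | 93.4% |
| 95-97% | 88.3% | 89.0% | 91.3% | 92.3% |
| 97-99% | 76.9% | 82.1% | 88.5% | 89.2% |

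Wilson averages 95.1% to 95.9% in all 16 cells from 80% upwards. Its lowest single-rate coverage at n = 78 is 93.3% within 80-90% and 91.6% within 97-99%. The Wald minima there are 89.2% and 54.3%.

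**Hand check of the worst point.** At n = 78 and a true rate of 99%, the chance of no non-responders is 0.99^78 = 0.457. The interval is then [100%, 100%] and misses. Coverage is therefore about 1 − 0.457 = 0.543.

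**Boundary examples, n = 78**

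- 78/78: Wald [100%, 100%]. The Wilson lower limit is 78 / (78 + 3.84) = 95.3%.
- 75/78: p = 0.9615, standard error 0.0218, upper limit 0.9615 + 0.0427 = 100.4%.
- 74/78: upper limit 99.8%.

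The chance of three or fewer non-responders at true rates of 90%, 95% and 98% is 4%, 45% and 93% for n = 78, and under 0.1%, 4% and 62% for n = 156. Capping limits at 100% removes the impossible values but leaves coverage unchanged, because the true rate lies below 100%.

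Coverage oscillates with the rate: Wald gives 95.0% at a rate of 95% with n = 156, but 90.3% at 90% with n = 93. No single threshold can be quoted.

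**If the intervals are for differences.** Exact two-sample enumeration with equal true rates, averaged over the four ranges from 80% to 99%:

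| Arms | Normal approximation | Newcombe |
|---|---|---|
| 156 vs 78 | 92.3-94.5% | 95.2-97.6% |
| 187 vs 93 | 91.8-94.6% | 95.2-97.3% |

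With unequal rates, 156 vs 78: 93.6% against 95.5% at (95%, 90%), and 89.8% against 97.4% at (99%, 95%).

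**The case against.** The strongest objection is that the harm needs two things the documents do not show: per-arm plain Wald intervals, and rates near 100%. The responder list is not readable, and unreadable text cannot be counted as missing from the plan. If a score interval was meant, there is no defect. This stands as a limit on the finding. It does not remove the point, because the readable sentence names a method without saying which form. A continuity-corrected Wald interval would not rescue the extreme case either: at n = 78 it averages 95.1% at 80-90% but 77.0% at 97-99%.

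Second, n = 78 at 97-99% is the worst cell. The control denominator may be nearer 93, and the Kysse arm loses less. That is correct, and the table shows it. It is also true that Wald coverage at n = 78 is already slightly low at moderate rates (94.4% at 50-60%); higher rates enlarge a small shortfall rather than create one.

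Third, the case for Newcombe is weaker. No difference in responder proportions is visible, the shortfall with equal rates is mild, and at 97-99% (156 vs 78) Newcombe over-covers by about as much (97.6%) as the normal approximation under-covers (92.3%). This stands, so Newcombe should apply only if differences are presented.

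Fourth, the SAP's randomised study is not the one in Protocol 4.1, which says "Approximately 50 to 60 subjects at 4 sites in Canada will be treated" in an open-label design. The consequence for that study is unknown.

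Last, no decision changes. This is conceded and sets the weight of the point.

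**Conclusion.** The concern holds as a conditional, minor point. Under the ordinary reading of the phrase, the stated method misses the stated 95% level. At rates of 80-90% the mean shortfall is 0.7 to 1.8 points across the SAP's arm sizes. At 97-99% it is 5.8 points at n = 187 and 18.1 points at n = 78. At 50-80% it is under one point. The conclusion assumes plain Wald intervals for single-arm rates, high true rates, and the arm sizes of the SAP's own study. Confidence is medium because the first two assumptions cannot be checked. Only secondary interval estimates are affected; the primary non-inferiority conclusion and the sample size do not change.

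**What to change.** Replace the sentence in SAP 2.4.4, before database lock, with:

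> Two-sided 95% CIs for responder proportions will use the Wilson score method; CIs for between-group differences in proportions, if presented, will use the Newcombe method.

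The cost is one sentence and a standard SAS PROC FREQ option. Wilson intervals are wider near 100%: at n = 78 and a true rate of 98% the mean width is 7.3 points against 5.3 for Wald. At lower rates the widths barely differ (13.3 against 13.1 points at 90%; 17.4 against 17.6 at 80%). Newcombe intervals are somewhat conservative at very high rates. If the authors already intend a score interval, naming it is all that is needed.

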2.4.5 Exploratory efficacy analysis

- Subgroup analysis of primary efficacy endpoint will be performed following the same method as described for the overall analysis, for the following subsets:
 - Study site
 - Fitzpatrick skin types (I-III, IV and V-VI)
 - Race

2.5 Safety Analysis

2.5.1 Extent of exposure

The number of subjects receiving initial treatment, touch-up treatment, and Week 48 retreatment respectively, will be presented by treatment group and treatment occasion (i.e. initial treatment or retreatment) as well as injection volume and other relevant injection characteristics, such as injection depth, injection method.

2.5.2 Adverse events

AE terms will be coded using MedDRA dictionary. A treatment-emergent AE (TEAE) is defined as an AE with a start date and time on or after the first study product injection. If relationship to treatment is missing, the event will be conservatively summarized as being related to study product. If intensity is missing, a separate category of missing intensity will be included in the summary table, and no imputation of intensity will be performed. Through the data cleaning process, all attempts will be made to avoid missing values for relationship and intensity.

All AEs will be presented in a by-treatment and by-subject listing, detailing the verbatim term given by the investigator, the preferred term (PT), system organ class (SOC), onset date, end date, intensity, outcome, relationship to study product, relationship to study product injection procedure, action taken with study drug, other action taken, affected treatment area, seriousness and criteria for seriousness. Serious AEs will be presented in a separate listing.

Time to onset of an AE will be derived as the start date minus date of most recent treatment. If the start date is missing, it will be assumed that the AE started on the day of most recent treatment.

Duration of an AE will be derived as the stop date minus the start date + 1. If the start date is missing, it will be assumed that the AE started on the day of most recent treatment. Missing stop date will not be imputed and therefore no duration will be calculated in these cases. Instead, the number of AEs that were ongoing at the end of the study will be given.

An overall summary of AEs will be presented by treatment. The summary will include the total number of events, frequency counts and percentages of subjects with:

- Any TEAE

- Any AE related to product and/or injection procedure
- Unrelated TEAEs
- No TEAEs reported

Summaries of related AEs (including the total number of events, frequency counts and percentages of subjects) will be displayed by treatment and treatment occasion according to the following:

- All AEs by SOC and PT in descending order of frequency (the combined frequency of both treatments)
- All AEs by SOC, PT, and maximum intensity (mild, moderate, or severe)
- All AEs by SOC, PT, and action taken (none, medical treatment, non-pharmacological treatment, subject withdrawn)

For related AEs, the number of days to onset and duration of event will be summarized by SOC and PT, using mean, SD, minimum, maximum, and median statistics.

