8.2.3 Recording instructions

Each subject should be questioned about AEs at each study visit following signing of informed consent. The question asked should be: "Since your last clinical visit; have you had any health problems?". Information on AEs can also be obtained from signs and symptoms detected during each examination or from a laboratory test, observations made by the study site personnel, subject diaries, or spontaneous reports from the subjects or their relatives.

Exceptions from AE reporting are normal fluctuations in pre-existing diseases. However, pre-existing illnesses that deteriorate shall be reported as AEs.

When an AE is related to a device deficiency (refer to Section 8.3), including technical device malfunction, the AE shall be recorded on the AE form/module in the eCRF and the technical complaint shall be reported separately on the clinical study complaint form.

Investigators, or other study site personnel, shall record all AEs in the eCRF, including:

- a) Event term (recorded in standard medical terminology and avoiding abbreviations)
- b) Affected area
- c) Start date (first day with symptoms)
- d) Stop date (last day with symptoms)
- e) Intensity (mild, moderate, or severe according to definition in Section 8.2.3.1)
- f) Seriousness (serious or not serious, according to definition in Section 8.2.3.2)
- g) Causal relationship to study product or study product injection procedure (yes or no)
- h) Action taken (none, medication treatment, non-pharmacological treatment, or other procedures/tests, subject withdrawn)
- i) Outcome of the AE (ongoing, recovered, recovered with sequelae, death, chronic/stable, not recovered at the end of the study)

The AE form/module in the eCRF must be signed and dated by the Investigator.

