8.2.3.1 Intensity

Intensity will be recorded for each reported AE. The following definitions of intensity are to be used:

Mild: Awareness of symptoms or signs, but easily tolerated (acceptable)

Moderate: Enough discomfort to interfere with usual activity (disturbing)

Severe: Incapacity to work or to do usual activity (unacceptable)

If the intensity changes within one day, the maximum intensity of the AE during that day shall be recorded.

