8.2.4 Reporting of adverse events

Adverse event reporting on each subject shall start at Visit 1 (Screening). The reporting shall continue during each follow-up visit (including telephone contacts and extra visits between planned visits) until the last scheduled visit in the study, Visit 6 (Follow-up at 8 weeks after last treatment).

All AEs, non-serious as well as serious, are to be reported as an AE in the eCRF.

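### The SAP's TEAE rule has no worsening clause and needs an onset time that the visible AE fields do not hold, so the three TEAE overview rows can be miscounted

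*SAP*

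**What the plan says.** The definition in SAP 2.5.2 reads: "A treatment-emergent AE (TEAE) is defined as an AE with a start date and time on or after the first study product injection". It is the only criterion given. Three rows of the overall AE summary in that section use it: *Any TEAE*, *Unrelated TEAEs* and *No TEAEs reported*. The fourth row, for AEs related to the product or the injection, is worded for AEs in general and is not limited to TEAEs.

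The by-subject AE listing in the same section shows "system organ class (SOC), onset date, end date, intensity, outcome", with no onset time. Time to onset and duration are both derived from dates. For those two derivations there is a rule for a missing date: "If the start date is missing, it will be assumed that the AE started on the day of most recent treatment". There is no rule for a missing time.

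SAP 1.5 refers to Section 8 of the clinical study protocol for the collection of safety data. Section 8 of the supplied protocol contains four relevant rules:

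- Collection starts before treatment (8.2.4): "Adverse event reporting on each subject shall start at Visit 1 (Screening").
- The onset item is a date (8.2.3): "Start date (first day with symptoms").
- On existing disease (8.2.3): "pre-existing illnesses that deteriorate shall be reported as AEs".
- On changing intensity (8.2.3.1): "If the intensity changes within one day, the maximum intensity of the AE during that day shall be recorded". Nothing visible covers a rise in intensity on a later day.

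**The concern.** Treatment-emergent counts are meant to capture what appears or gets worse once treatment has started. A rule based on start alone captures only what appears. If AE records can be open at the time of injection, a later worsening of such an event has no route into the TEAE rows, and a subject who did worsen may be reported as having had no TEAE.

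The second difficulty is practical. The rule compares an event's date and time with the injection, but the visible fields give only a date. On the injection day the date alone cannot separate an event that began that morning from one that followed the injection. Protocol 8.2.9 anticipates injection-related events such as bruising, swelling, pain and tenderness, so that day deserves an explicit rule.

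**Working it through.** This is a question of definition; the plan gives no figure to reproduce. Applying the SAP 2.5.2 rule to the recording rules in protocol 8.2.3, 8.2.3.1 and 8.2.4 gives four cases.

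| Case | Recorded start | TEAE? |
|---|---|---|
| 1. Pre-existing illness deteriorates after injection, dated to the deterioration | On or after injection | Yes |
| 2. Same event, dated to the first symptoms of the illness | Before injection | No |
| 3. AE begins between screening and injection, stays one record, intensifies on a later day | Before injection | No |
| 4. AE begins on the injection day, date only | Same date as injection | Cannot be decided |

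**Cases 1 and 2.** The clinical event is the same, and only the dating differs. Protocol 8.2.3 makes the deterioration reportable but does not say whether its start is the day of deterioration or the first day of symptoms.

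**Case 3.** The start date precedes injection, and the intensity rule does not reach a change on a later day. If the event is unrelated, it is missing from *Any TEAE* and *Unrelated TEAEs*. If it is related, it is missing from *Any TEAE* but counted in the related-AE row. A subject with no other event can then appear both in the related-AE row and under *No TEAEs reported*. The same holds for case 2.

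**Case 4.** The error has no fixed direction. Counting all such events by date would include some that preceded injection; leaving them out would lose some that followed it.

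**Size per subject.** SAP 1.1.1 plans about 187 Kysse and 93 control subjects. For one affected subject with no other event, the change in an arm's percentage is 1 divided by the number in the arm:

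- Kysse: 1/187 = 0.53%, about 0.5 percentage points.
- Control: 1/93 = 1.08%, about 1.1 percentage points.

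The documents do not give the number of AEs open at injection, so no total can be calculated.

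**Outputs that do not use the TEAE rule.** These are the related-AE endpoint (SAP 1.6), the related-AE tables by SOC and PT, intensity and action taken (SAP 2.5.2), the diary summaries (SAP 2.5.3) and the listing: "All AEs will be presented in a by-treatment and by-subject listing".

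**The case against.** The strongest answer is that protocol 8.2.3 already handles worsening. Deterioration of a pre-existing illness is itself an AE, and if it is dated to its own first day it meets the SAP definition. This stands, and it limits the point. A reader might infer that any condition present before injection that worsens afterwards is dropped. The documents do not support that: case 1 is counted. What remains is the unstated dating convention (case 2) and the AE that opens before injection and stays one record (case 3).

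Second, the main safety outputs are unaffected. The SAP's AE endpoint concerns related AEs, and the related-AE tables carry no TEAE restriction. A worsening judged related appears there, every AE is listed by subject, and the common injection-site symptoms are also summarized from the 30-day diary. This stands too.

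Third, a reader might infer that onset time is not collected at all. The documents do not show that. The list in protocol 8.2.3 is introduced as inclusive, the SAP names listing columns rather than database fields, and the eCRF is not supplied. An unseen time field cannot be excluded.

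Fourth, the two documents describe different designs. Protocol 4.1 describes an open-label study of about 50 to 60 subjects, while SAP 1.1.1 describes a randomized, evaluator-blinded study of about 280. The protocol's AE rules may not be those that govern this SAP. This weakens the mechanism in cases 2 and 3, and equally weakens any reliance on protocol 8.2.3 as a remedy. The missing worsening clause and the date-only listing rest on SAP 2.5.2 alone.

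**Conclusion.** The point holds within narrow limits. As written, SAP 2.5.2 leaves out of the TEAE rows an AE that is open before injection, kept as one record and worse afterwards. It counts a deterioration of a pre-existing illness only if the site happens to date it to the deterioration. From the visible fields, it cannot be applied to injection-day events whose order relative to the injection is unknown.

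A reader might infer that TEAE counts can only be too low. That is true of the worsening gap but not of the injection-day gap, which can go either way.

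The effect is confined to three overview rows, at about 0.5 points (Kysse) or 1.1 points (control) per affected subject with no other event. This takes the planned arm sizes as denominators; the actual safety population may differ. The number of affected subjects is unknown. The conclusion on worsening also assumes that AEs are collected before injection under the SAP's own protocol, as they are in the supplied one.

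**What to change.** In SAP 2.5.2:

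- Define a TEAE as an AE whose onset date is on or after the date of first injection, or an AE or pre-existing condition that increases in intensity on or after that date.
- Count an injection-day event as a TEAE unless the record shows that it preceded the injection.

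In the eCRF completion instructions:

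- Record a worsening after injection as a new AE dated to the day of worsening, and use that date for time to onset and duration. This also gives time to onset a usable value; the SAP's formula subtracts the most recent treatment date, and none precedes an event that began before the first injection.

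The changes should be settled before database lock, together with confirmation of which protocol's AE rules apply to this SAP. The cost is a SAP wording change, an instruction to sites and some split AE records, since a later rise in intensity cannot be seen in a single record. TEAE counts will be slightly higher, and a split record adds to the number of events.
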